12.2. Patient demographic and other baseline characteristics

Patient demographic and baseline characteristic data will be described by means of absolute and relative frequencies for categorical variables and mean, standard deviation minimum and maximum, for continuous variables. Categorical variables will include sex, race, ethnicity, country, date of birth, age at RIS, etc.

12.3. Analysis of other variables

To validate the association between incidentally identified anomalies within the CNS that are highly suggestive of MS and seminal demyelinating events, systematically acquired environmental exposure, clinical, and radiological, data will be assimilated in an effort to identify significant risk factors. We will evaluate the time from the initial MRI revealing incidental anomalies to the first demyelinating event (acute or initial symptom resulting in a progressive clinical course) or new MRI focus utilizing Kaplan-Meier survival analyses. Log-rank tests will be used to compare survival data between groups at univariate analysis. Multivariate Bayesian Cox regression models will be created to assess the independent predictive value of demographic characteristics (i.e. sex, ethnicity, age at the time of RIS diagnosis), clinical data (i.e. MS family history, occult neurological examination findings, environmental exposure data, CSF profiles, cognitive performance, etc.), and imaging data (i.e. number of brain MRI lesions, the presence of gadolinium enhancing lesions, geographical distribution of lesions, involvement of the spinal

cord, brain atrophy, etc.) on the time to the first symptomatic event. The association of each covariate with time to the first clinical symptom will be quantified by hazard ratios (HR) along with their 95% confidence intervals (CI). Assessments to determine differences between centers will also be performed with statistical adjustments planned for subsequent analyses depending upon the obtained results. Corrections to co-variables will be made when necessary if baseline differences are detected.

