5.2 Central Clinical and Imaging Units

To accurately identify subjects with RIS, formal units will be created to review data prior to study entry.

5.2.1 Core Clinical Unit:

A Core Clinical Data Unit, led by [name], will be formed and comprised of a prominent international collaborator and trained MS specialist. This group will evaluate clinical information from both existing and new cases within partnering centers, including results from para-clinical studies (i.e. blood work, CSF, electrophysiological studies, etc.) to ensure that subjects accurately fulfill criteria for study entry. In addition, this group will be responsible for adjudicating all neurological events and post-attack clinical data during the study period. If a discrepancy exists between reviewers following the independent review of submitted cases, [name] will provide a decision on the final classification. The Core Clinical Unit will unify all screening data (including conclusions from the Central Imaging Unit (below)) and will notify participating site PIs when entry criteria are met for potential study participants.

5.2.2 Central Imaging Unit:

A Central Imaging Unit will be formed and will be comprised of a board certified neuro-radiologist and MS specialist with neuro-imaging expertise. The MS specialist will confirm screened cases for study entry. MRI scans from subjects will be independently reviewed by the MS specialist and neuro-radiologist and determinations made if subjects fulfill MRI criteria for RIS. If a discrepancy exists between the two reviewers following the independent review of a case the MS specialist with neuro-imaging expertise will provide a decision on the final classification. The MS specialist with neuro-imaging expertise will also be responsible for

ensuring that a uniform protocol (“Dummy scans”) is implemented at specified sites for the collection of uniform, multi-center data for post processing. In addition, this group will evaluate all MRI studies of the CNS for interval change (i.e. new and enlarging T2 lesion(s), gadolinium enhancement) during follow-up imaging studies and imaging studies acquired during clinical events. At End of Study, changes in T2-lesion volumes, and brain atrophy (SIENA) will be determined.

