Standardized MRI studies of the brain will be performed at weeks 0 ,96, 144 or EOS; an additional MRI will be obtained at week 46 for those patients enrolled at the UTSW site only. Clinical imaging studies of the brain and/or spinal cord performed during or immediately following the onset of a clinical exacerbation will be performed at the discretion of the site PI with scan costs covered under the medical standard of care. A clinical MRI of the cervical spinal cord with and without contrast will be recommended to study participants at week 0 and week 144 as medical standard of care.

Participants who cannot receive contrast due to allergic reaction or abnormal blood counts will not be excluded from the study. Their imaging studies without contrast will be accepted.

All reported acute or progressive clinical events will be adjudicated by the Central Clinical Unit. Clinical visits due to suspected exacerbations associated with CNS demyelination, and associated diagnostic studies and treatments, will be covered under the medical standard of care by third party payers. A recommendation to re-evaluate the patient within 3 months following the clinical event to assess for extent of recovery will be made.

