5.5 Database fields

The following data will be captured in this study via electronic data capture (EDC).

Clinical Data: Comprehensive demographic data (i.e. date of birth, sex, race and ethnicity, etc.) and clinical data (i.e. date of first clinical visit, reason for the initial MRI scan, findings from the patient's clinical examination (*to include vital signs*), Visual Systems Tests (low vision contrast charts, ocular coherence tomography (OCT)) CMP and CBC results, cerebrospinal fluid test results, new onset clinical attacks, extent of recovery, etc. will be obtained from face-to-face clinical visits and existing medical records. Cognitive/Functional assessments (*EDSS, expanded MSFC (Timed 25-FT Walk (T25-FW), 9-Hole Peg Test (9-HPT), Paced Auditory Serial Addition Test (PASAT-3 (3-second interval pause)), Symbol Digit Modalities Test (SDMT)*), will also be performed. Please refer to Appendix 1 – Cognitive/Functional Assessments

Patient Reported Surveys: Surveys containing questions related to Demographics, Family History, Lifestyle, Environment, and Environmental Exposure and the Neuro Quality of Life Questionnaire (*Neuro-QOL data*), will be completed by each study participant ; included will be inquiries into previous illnesses, the use of over-the-counter supplements, diet, occupational histories, exposure to vaccinations, etc. Please refer to Appendix 2 – Patient Reported Surveys.

Adverse events as well as concomitant medications will be collected and reported. All data collected for clinical assessments will be submitted via EDC and shared with Biogen. At the time of any patient withdrawing from the trial, an attempt will be made to determine the reason for discontinuation.

Radiological Data: Comprehensive radiological data will be collected from RIS subjects. Data to be incorporated into the study database include the date of the first MRI scan demonstrating anomalies within the brain that are suggestive of MS, number of lesions, lesion location, the presence of contrast enhancing lesions, the number of contrast enhancing lesions, changes observed between MRI studies, etc. In addition, data from the clinical MRI study of the cervical spine obtained at screening or Month 0 and at EOS will be incorporated if completed.

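### The risk-factor survival analysis in section 12.3 starts the clock at the first incidental MRI without delayed entry at randomization, so time free of a clinical event by selection is counted as time at risk

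*Protocol*

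**What the plan says.** Section 12.3 sets out a search for risk factors. It states: "We will evaluate the time from the initial MRI revealing incidental anomalies to the first demyelinating event", and extends the endpoint with "or new MRI focus utilizing Kaplan-Meier survival analyses". On group comparisons it says: "Log-rank tests will be used to compare survival data between groups at univariate analysis". Multivariable Bayesian Cox models follow, "on the time to the first symptomatic event", with no time origin named. Delayed entry, left truncation and entry time appear nowhere in the protocol.

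The primary analysis (Synopsis; section 3.1) runs from randomization.

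On imaging, section 5.2.2 has the central unit "evaluate all MRI studies of the CNS for interval change (i.e. new and enlarging T2 lesion(s), gadolinium enhancement) during follow-up imaging studies". Section 5.5 records the "date of the first MRI scan demonstrating anomalies within the brain that are suggestive of MS" and also "changes observed between MRI studies", without saying which scans are compared. Section 5.3 fixes the study scans: "Standardized MRI studies of the brain will be performed at weeks 0 ,96, 144 or EOS".

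**The concern.** A subject joins this trial only by reaching randomization without a clinical demyelinating event. A person who had one after the first MRI is no longer RIS and does not enter. On a clock that starts at the first MRI, the stretch up to randomization can therefore contain no clinical event, by selection. If it counts as time at risk, the event rate is diluted and event-free survival since the first MRI is overstated.

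The group comparison suffers when the MRI-to-randomization gap differs between groups: the group with longer gaps looks protected. Section 12.3 considers factors such as center and age at RIS diagnosis, which could be related to the gap. At stake are the reported conversion risk and the list of risk factors, not the treatment effect.

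**Working it through.** **Inputs from the protocol.** Initial MRI in 2009 or later (section 6, inclusion 2); existing as well as new cases screened (5.2.1); last patient in 30 September 2019, last patient out 31 March 2021 (section 13); last scheduled visit week 144 and about 90 subjects (5.3). The plan gives no figure for this analysis, so there is none to reproduce.

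**Assumptions.** Constant clinical hazard h, mainly 0.10 per year; gap uniform on 0 to G years; new foci at 0.1, 0.2 or 0.4 per year; follow-up uniform on 1.5 to 2.77 years.

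**1. Possible gap.** From 1 January 2009 to 30 September 2019 is 10.74 years. On-study follow-up is 1.5 years for the last patient in and 144/52 = 2.77 years to week 144.

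**2. Is the gap event-free?** Exclusion 3 does not settle it, since it covers only symptoms before the imaging. The RIS definition (section 2.1), inclusion 5 and an outcome defined as the first event after randomization together imply it.

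**3. Clinical event: size of the bias.** At time t since MRI only the share already randomized can have an event, so the naive hazard is about h × (share randomized by t). Ignoring depletion by events and censoring, the naive cumulative hazard to 3 years is h(3 − G/2) if G ≤ 3 and 9h/(2G) if G > 3. The truth is 3h. For h = 0.10 the true risk is 1 − exp(−0.30) = 25.9%.

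| G (years) | Naive cumulative hazard | 1 − exp(−·) | Simulated naive risk |
|---|---|---|---|
| 0.5 | 0.275 | 24.0% | 24.0% |
| 1 | 0.250 | 22.1% | 22.2% |
| 2 | 0.200 | 18.1% | 18.2% |
| 4 | 0.1125 | 10.6% | 9.8% |
| 8 | 0.05625 | 5.5% | 4.8% |

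Simulated at h = 0.05 (true 14%): 13, 12, 9, 5 and 3%. At h = 0.15 (true 36%): 34, 31, 26, 14 and 7%. With delayed entry at h = 0.10 the estimate is 25.7-26.4%.

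**4. Adding new MRI foci.** Freedom from new foci is not an entry condition, so the result depends on which foci count. The true composite 3-year risk is 45 / 59 / 78% for the three focus rates.

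| Reading | Gaps up to 2 years | Gaps up to 4 years |
|---|---|---|
| B: foci before randomization count, dated when they arise | 39 / 55 / 75% | 34 / 51 / 73% |
| C: only foci after week 0 count | 32 / 44 / 61% | 18 / 25 / 35% |
| D: as B, but dated at the study scan that shows them | 35 / 49 / 67% | 24 / 35 / 50% |

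Reading D assumes no scan between the first MRI and week 0. With gaps up to 0.5 year it overshoots (49 / 66 / 84%), an effect of scan dating.

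**5. Log-rank, factor with no effect, 45 against 45, h = 0.10.** Share of tests significant at 5% (A = clinical event only; B and C by focus rate, D as a range over the rates):

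| Gaps in the two groups (years) | A | B | C | D |
|---|---|---|---|---|
| 0-2 vs 0-2 | about 5% | about 5% | about 5% | about 5% |
| 0-1 vs 0-2 | 9% | 7 / 5 / 6% | 13 / 16 / 30% | 13-14% |
| 0-2 vs 0-4 | 20% | 9 / 6 / 5% | 33 / 50 / 71% | 26-55% |
| 0-1 vs 0-4 | 36% | 15 / 11 / 8% | 65 / 82 / 96% | 56-87% |
| 0-2 vs 0-8 | 60% | 18 / 10 / 7% | 87 / 97 / 100% | 91-100% |

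Under A the median hazard ratios for the four unequal settings are 0.75, 0.57, 0.41 and 0.26, where the truth is 1. Delayed entry or randomization as origin gives 4-6% and hazard ratios of 0.97-1.02.

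**6. A second set of assumptions** (clinical event only, hazard 0.07, follow-up 1.5-3 years, gaps up to 5 years): naive 5-year event-free proportion 0.85 against a true 0.705; 0.71 with delayed entry. With gaps up to 5 or 10.75 years in one group and half that in the other, the naive hazard ratio is 1.6-1.9 for the shorter-gap group, and the false-positive rate at n = 90 is 15-23%.

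**The case against.** - **It may be left to the SAP.** Time since first MRI is a legitimate scale, Kaplan-Meier and log-rank both admit delayed entry, and an unseen SAP could add it. But the protocol fixes the origin and names the plain estimators; following it as written gives a biased curve.
- **The endpoint is a composite.** If foci are counted from the first scan (reading B), false-positive rates are only 5-9% in the two milder settings. This stands for that reading. Section 12.3 does not choose it, and reading C is worse than the clinical event alone.
- **Unequal gaps are undocumented.** True: with equal gaps the test keeps its level, and no figure here establishes the size for this trial. The curve is biased either way.
- **The Cox models may be unaffected.** The Synopsis places the same Cox text after an analysis from randomization, so they may use that origin. This stands; they are affected only if they use the MRI clock.
- **Delayed entry is noisy.** For the 3-year clinical risk with n = 90, root mean squared error, naive against delayed entry, is 0.055 against 0.068 (hazard 0.05, gaps up to 2 years), 0.089 against 0.087 (0.10, up to 2) and 0.164 against 0.112 (0.10, up to 4). At short gaps the naive estimate can thus have the lower total error, but its bias does not shrink with more subjects.
- **The selection is inferred.** No criterion expressly bars an event between MRI and randomization. The inference is nonetheless firm.

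**Conclusion.** The concern holds. As written, the section 12.3 curve overstates freedom from a clinical event since the first MRI. At an assumed 0.10 per year the 3-year risk of 26% would read 18% with gaps up to 2 years and 10% with gaps up to 4. The log-rank test goes wrong only if gaps differ by risk factor, which is an assumption. For the composite, the bias runs from small to very large depending on a counting rule the section leaves open. All hazards, gap distributions and focus rates are assumed. The primary analysis and the treatment comparison are untouched. For a risk-factor screen in about 90 subjects this is a minor to moderate defect, worth correcting because the correction is cheap.

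**What to change.** In section 12.3 choose one of two routes:

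1. Keep the first-MRI clock, enter each subject into the risk set at randomization, and count new foci against the week-0 scan.
2. Make randomization time zero and put time since first MRI into the models as a baseline covariate.

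Under either route, report the clinical event separately from the composite and state which origin the Cox models use.

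This takes about three sentences and an entry-time argument in the survival code. The first-MRI date is already a database field and randomization is at week 0.

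Route 1 has a price:
- About 11, 5 or 3 of 90 subjects are at risk at 3 months for gaps up to 2, 4 or 8 years, so numbers at risk should be shown.
- The standard deviation of the 3-year clinical risk is about 8-9, 11-12 or 14-15 percentage points; for the composite it is 6-9, 8-12 or 12-16.
- Entry time must be unrelated to risk, given time since MRI.
- MRI change before randomization is set aside. The share of subjects with such a focus is 1 − (1 − exp(−rG))/(rG), where r is the focus rate: 9-31% for G = 2 and 18-50% for G = 4.

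Route 2 avoids the sparse early risk set but asks a somewhat different question.

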13. TIMELINE ESTIMATE

- Contracting completion to IRB approval: 7 months
- Last patient in: September 30, 2019
- Last patient out: March 31, 2021
- Study completion and submission of final manuscript for publication: September 1, 2021

14. BIOMARKER ASSESSMENTS

Whole blood samples and cerebrospinal fluid (CSF) for biomarker analysis may be collected from all subjects and transferred to UT Southwestern biorepository. A portion of the biosamples will be stored at -80°C prior to being shipped on dry ice to Biogen in batches every quarter where they will be centrally analyzed.

- Whole blood may be collected at week 0, week 48, week 96, week 144/or EOS,, Early Withdrawal and at relapse.
- CSF may be collected at week 0, week 48, week 96, and week 144/or EOS.

A total of approximately 400mL (25-27-30 tablespoons) of whole blood may be collected for the scheduled visits. Approximately 71 mL (5 tablespoons) of whole blood may be collected at each relapse or early withdrawal.

Those subjects who are unable or unwilling to contribute CSF samples will still be included in the study. Failure to acquire CSF will not be considered a protocol deviation.

The samples collected may be utilized to identify or verify putative prognostic and predictive markers associated with disease and markers of therapeutic response to DMF treatment. Baseline and dynamic (on-study) clinical disease characteristics and associated biomarker data may be utilized to predict subsequent disease worsening (severity), identify high-risk patient subgroups, and identify predictors of response to DMF treatment.

Specifically, whole blood, collected in EDTA coated and PAXgene tubes, and CSF, collected in PAXgene tubes, will be collected for future analysis of DNA, RNA, and protein biomarkers, as follows:

- Deoxyribonucleic acid (DNA) from whole blood collected at Baseline may be used for an exploratory pharmacogenomics analysis. Experience with treatment in MS shows that there is heterogeneity in clinical response, and some of the heterogeneity may be associated with genetic variants in patients. Genome-wide studies have identified approximately 50 single-nucleotide polymorphisms (SNPs) as MS-associated loci. DNA may be used for genome-wide or candidate gene SNP analysis. Allelic variants at SNP loci will be tested for association with efficacy and treatment response.
- Ribonucleic acid (RNA) from whole blood and CSF cell pellet may be used for analysis of gene expression. RNA may be used for genome-wide or candidate gene expression studies. The transcriptional profile will be used to understand the heterogeneity and to define the sub-structure of the MS patient population. Additionally, potential predictive

markers at Baseline through identification of transcript pattern that may predict disease/treatment outcome may be assessed.

- Serum and CSF samples may be used to determine the levels of markers of inflammation, pro- and anti-inflammatory cytokines related to T helper 1 (Th1)/Th2 and Th17 pathways, chemokines, and other proteins known to play a role in the transmigration of leukocytes and neurodegeneration. This targeted protein list is not all encompassing and may be expanded to include markers related to disease, efficacy or mechanism of action of DMF as more knowledge becomes available.
- In addition, serum and CSF samples will be stored for future exploratory analyses at UT Southwestern.

APPENDIX 1: Cognitive/Functional Assessments

EDSS, expanded MSFC (Timed 25-FT Walk (T25-FW), 9-Hole Peg Test (9-HPT), Paced Auditory Serial Addition Test (PASAT-3 (3-second interval pause)), Symbol Digit Modalities Test (SDMT)

- See attached

APPENDIX 2: Patient Reported Surveys

Surveys containing questions related to Demographics, Family History, Lifestyle, Environment, and Environmental Exposure and the Neuro Quality of Life Questionnaire (Neuro-QOL data), will be completed by each study participant ; included will be inquiries into previous illnesses.,

- See attached
